#### 9.4.1 Analysis of Exploratory Endpoints:

##### Tumor Microenvironment Modulation and Immunologic Response

The overarching aim of these studies is to establish baseline levels for, and measure changes in immunological pathways after treatment. Little is known about baseline levels for these variables in biliary tract cancer, let alone changes after treatment, and if the primary and secondary aims are successful, these investigations will establish a biological foundation on which to build in follow up studies that will include the following comparisons with the aim of correlating these observed changes with treatment response, and toxicity:

- Baseline versus on-treatment expression of PD-L1
- Baseline versus on-treatment of immune markers quantifying ratio of CD8+ T effector cells and CD4+FoxP3+ T regulatory cells, and major histocompatibility complex (MHC) class I expression.
- Baseline versus on-treatment immune markers of T cell function and quality (see correlative studies sections above)

- Baseline versus on-treatment circulating immune cells (Tc, TH1, TH2, TH17) and cytokine profiles in peripheral blood by flow cytometry

Immunological variables will be examined in plots and summary statistics, to characterize distributions, identify outliers and other potential problems in the data. Joint exploratory analysis will identify associations and potential interactions. Variables may be transformed on the basis of these investigations, to reduce skewness, minimize the influence of outliers and/or to regularize relationships between predictors and response for better model fit. Exploratory analysis of the molecular markers, including visualizations and statistical summaries such as hierarchical cluster analysis, heat maps, multidimensional scaling, and principle component analysis will offer important views of the structural characteristics of the expression data.

Response will be described categorically, and associations between response and immunological variables will be characterized, in each arm, using multivariate logistic regression models, with adjustment for clinical and pathological co-variates that may be associated with response. Estimated effects will be reported with standard errors and confidence intervals.

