### 1.2 Secondary Objectives

- 1.2.1 To assess the safety and tolerability of combination of atezolizumab and CDX-1127 (varlilumab) with or without cobimetinib in patients with unresectable, pre-treated biliary cancers.
- 1.2.2 To assess overall survival (OS) of patients with unresectable, pre-treated biliary cancers treated with the combination of atezolizumab and CDX-1127 (varlilumab) with or without cobimetinib.
- 1.2.3 To determine the effect of combination atezolizumab and CDX-1127 (varlilumab) +/- cobimetinib on T cell subpopulations systemically and intratumorally.

[REDACTED]

1.3.1 [REDACTED]

1.3.2 [REDACTED]

1.3.3 [REDACTED]

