### 2.4.2 PD-L1 expression

Exploratory biomarker assessed with IHC using SP142 [Spring, Biosciences] in collaboration with [name].

Across tumors of multiple histologic type, PD-L1 expression measured by immunohistochemistry (IHC) is a well-characterized biomarker for predicting patient response with PD-1/PD-L1 blockade (Patel & Kurzrock, 2015). However, the utility of this biomarker in biliary tract cancers in the context of combination immunotherapy, and the effect of MEK inhibition on PD-L1 expression, are unknown. In theory, upregulation of PD-L1 may reflect a tumor with potential for immune reactivity, as various T cell derived cytokines (i.e. interferon-gamma) are well-characterized positive regulators of PD-L1 expression. We will use a previously validated technique and assay to assess this exploratory biomarker (Mody *et al.*, 2016; Rimm *et al.*, 2017)

We hypothesize that patients with increased expression of PD-L1 at baseline will be more likely to respond to therapy regardless of treatment arm.

We hypothesize that treatment with atezolizumab and CDX-1127 (varililumab) will increase PD-L1 expression and TILs as compared to each patient's baseline, and that addition of cobimetinib to this combination will induce further increase in both PD-L1 and TIL in patient tumors.

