#### 2.4.5 Circulating immune markers in peripheral blood (Th/Tc, phenotype, naïve/memory and exhaustion markers [PD-1, CTLA4, ICOS, BTLA, LAG3, TIM-3]) and plasma cytokines (Th1/Th2/Th17).

Administration of the immunomodulatory agents included in this clinical trial has potential to elicit potent systemic shifts in cytokines that occur downstream of T cell activation. Each therapeutic antibody included in the regimen has potential to induce immune cell activation. Similarly, MEKi may be particularly adept at modulating cytokine secretion from tumor or stromal cells that lead to local or systemic shifts in Th1, Th2 and Th17 profiles.

Since, in many cases of BTC, it is difficult to obtain enough biopsy tissue to reflect all tumor heterogeneity and to properly study TIL phenotype and location *in situ*. Thus, increasing studies have focused on studying the profile of blood circulating immune cells to predict the immunotherapy response.

This trial provides a unique opportunity to conduct exploratory analysis to assess quantitative and qualitative changes in peripheral T-cell response and evaluate T-cell quality by characterizing cellular markers associated with poly-functionality, exhaustion, memory, and activation. The interactions between CD27 agonism and PD-L1 and/or MEK inhibition on systemic immune biomarkers have not been carefully examined and will provide a comprehensive dataset that can be integrated with clinical outcome measures including survival, response, or toxicity (Sanjabi & Lear, 2021)

We hypothesize a greater frequency of circulating T cells with memory phenotype will be evident in patients receiving cobimetinib in combination with atezolizumab and CDX-1127 (varlilumab) as compared to patients treated with atezolizumab and CDX-1127 (varlilumab) alone. In addition, we predict that patients who respond to treatment will have fewer inhibitory checkpoint receptors concurrently expressed on their circulating CD4+ or CD8+ T cells and a lower frequency of circulating cytokines or cells that are associated with an IL-17-driven immune responses.

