#### Correlative Secondary Endpoints:

##### Change in T-Cell populations (TILs):

The density of CD8+ T cells in each treatment group, at baseline and after treatment, will be visualized using boxplots, and described using summary statistics including means and standard deviation presented with 95% confidence intervals. A student t-test or nonparametric Wilcoxon rank-sum test will be used to determine whether the increase in CD8+ T cells is greater in treatment arm B (combination atezolizumab and CDX-1127 (varlilumab) plus cobimetinib) than in treatment arm A (atezolizumab and CDX-1127 (varlilumab)).

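### The systemic half of secondary objective 1.2.3 has no between-arm analysis: circulating T cells are listed only as a baseline-versus-on-treatment comparison under exploratory endpoints

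*Combined protocol and SAP*

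**What the plan says.** Section 1.2, objective 1.2.3, is a secondary objective. It concerns the effect of the doublet with or without cobimetinib "on T cell subpopulations systemically and intratumorally".

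Section 2.4 states what cobimetinib is expected to add:
- Blood (2.4.5): "We hypothesize a greater frequency of circulating T cells with memory phenotype will be evident in patients receiving cobimetinib", with the doublet alone as comparator.
- Tumour PD-L1 and TIL (2.4.2): "addition of cobimetinib to this combination will induce further increase in both PD-L1 and TIL in patient tumors".
- Tumour CD8+ count and CD8:Treg ratio (2.4.1): the doublet's effect is expected to be larger with cobimetinib.
- Tumour microenvironment (2.4.3): effector T cells, Tregs, MHC-I and exhaustion markers are set against baseline or the doublet. The section also says that paired biopsies will be used to look at arm effects on these changes.

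Section 9.4 has one between-arm immune analysis, for tumour CD8+ density. A t-test or Wilcoxon rank-sum test "will be used to determine whether the increase in CD8+ T cells is greater in treatment arm B". (That sentence calls the triplet arm B. Section 6.1 and the study calendar give cobimetinib to Arm A, so the labels need reconciling.)

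Section 9.4.1 lists the other markers as comparisons over time:
- "Baseline versus on-treatment expression of PD-L1";
- "Baseline versus on-treatment of immune markers quantifying ratio of CD8+ T effector cells and CD4+FoxP3+ T regulatory cells", together with MHC class I;
- markers of T-cell function and quality;
- "Baseline versus on-treatment circulating immune cells (Tc, TH1, TH2, TH17) and cytokine profiles in peripheral blood by flow cytometry".

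The stated purpose of the list is to relate these changes to response and toxicity. The only model named is a logistic regression of response on the markers, fitted separately in each arm.

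**The concern.** The doublet arm is the randomised control for everything the two arms share: both antibodies, the passage of time and repeat sampling. A change from baseline in the triplet arm contains all of that plus any cobimetinib effect. Only a comparison of the arms separates the two.

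Section 9 makes that comparison for tumour CD8+ density and for no other immune marker. The gap is plainest for circulating T cells. They belong to a secondary objective, they carry a directional triplet-versus-doublet hypothesis, and their blood samples are mandatory at baseline, C1D21, Week 12 and end of treatment (5.1 and 5.8). Yet they appear only under exploratory endpoints, with no arm term. At stake is whether the trial reports a randomised estimate of cobimetinib's systemic effect, or two separate time trends that a reader must compare by eye.

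**Working it through.** **Step 1. Match each stated cobimetinib hypothesis to an analysis in Section 9.**

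| Marker | Where cobimetinib is expected to add | Between-arm analysis in Section 9 |
|---|---|---|
| Tumour CD8+ density (TIL) | 2.4.1, 2.4.2 | Yes, 9.4 |
| CD8:Treg ratio | 2.4.1 | None; over time only, 9.4.1 |
| PD-L1 | 2.4.2 | None; over time only, 9.4.1 |
| MHC-I, exhaustion markers | 2.4.3 | None; over time only, 9.4.1 |
| Circulating memory T cells | 2.4.5, objective 1.2.3 | None; over time only, 9.4.1 |

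The response models in 9.4.1 do not fill the gap. They ask whether a marker relates to response within an arm, not whether cobimetinib moved the marker. The joint exploratory analysis mentioned there names neither an arm term nor a quantity to be estimated. The circulating-cell item names Tc, TH1, TH2 and TH17. Memory subsets would have to come in through the item on T-cell function and quality, which refers back to the correlative sections.

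**Step 2. What a between-arm contrast could detect.** The plan has no figure of its own to reproduce here. Inputs: 32 patients per arm (Section 9.2). Two-sided 0.05, 80% power and the smaller numbers of pairs are assumptions, since the documents set none for these markers. The unit is the SD of the change.

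- Between arms: (1.960 + 0.842) × √(2/n)
- Within one arm: (1.960 + 0.842) / √n

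| Pairs per arm | Between arms | Within one arm |
|---|---|---|
| 32 | 0.70 SD | 0.50 SD |
| 24 | 0.81 SD | 0.57 SD |
| 16 | 0.99 SD | 0.70 SD |

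The ratio is √2 throughout. That is the price of asking the randomised question.

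**Step 3. Illustration only: why two within-arm results are a poor substitute.** Suppose both arms have the same true change, so cobimetinib adds nothing, and each arm is tested separately with a paired t-test at two-sided 0.05. With q the power of one such test (noncentral t), the chance that exactly one arm is significant is 2q(1 − q).

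| Pairs per arm | q at 0.5 SD | Exactly one significant | q at 0.3 SD | Exactly one significant |
|---|---|---|---|---|
| 15 | 0.438 | 49% | 0.192 | 31% |
| 20 | 0.565 | 49% | 0.247 | 37% |
| 25 | 0.670 | 44% | 0.302 | 42% |
| 32 | 0.782 | 34% | 0.376 | 47% |

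At 0.5 SD the triplet arm alone would be significant in half of the discordant cases, 17–25%. A direct between-arm test would be falsely positive 5% of the time. Effect sizes and pair numbers are assumptions.

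**The case against.** **The plan does intend arm comparisons.** Section 2.4.3 says so for the tumour microenvironment, and the biomarker table in 5.8 describes the tissue and blood assays as exploring the doublet with and without cobimetinib. This stands in part. A reader might infer that the cobimetinib hypotheses are never tested, but the documents do not support that: the TIL half of the 2.4.2 hypothesis is tested in 9.4, and for the other tumour markers what is missing is an analysis for a stated intent. For blood, the 5.8 wording names no comparison.

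**No within-arm significance rule is stated.** Correct. A reader might infer that cobimetinib will be judged by one arm reaching significance and the other not. Section 9.4.1 specifies no test, p-value or alpha for these changes; it plans plots, summaries, clustering and response models with confidence intervals. The Step 3 percentages therefore show a hazard of informal reading, not an error rate of this plan. Blood is mandatory and 32 patients per arm are planned, so the 32-pair row is the closest to the circulating markers.

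**These analyses are exploratory, and the 1.3 objectives are redacted.** Both are true, and nothing can be concluded about objectives that cannot be read. Neither explains the blood gap, because objective 1.2.3 is legible and labelled secondary.

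**The 9.4.1 list may describe follow-up studies.** Its sentence can be parsed that way. On that reading still less is specified for circulating T cells in this trial.

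**Conclusion.** The concern holds in a limited form. As written, Section 9 gives no randomised answer on the systemic effect of cobimetinib, although secondary objective 1.2.3 and Section 2.4.5 ask for one. For PD-L1, CD8:Treg ratio and MHC-I, an intended arm comparison has no method behind it.

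This is a cheap improvement, not a threat to the trial: the co-primary endpoints and the tumour CD8+ test are unaffected. The conclusion rests on the wording of Sections 1.2, 2.4 and 9 and on no disputed figure. The size of what could be learned is modest. About 0.70 SD is detectable with 32 pairs per arm, and less precision is available where biopsies are missing, so the added analysis would be estimation rather than confirmation.

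**What to change.** In 9.4, under secondary endpoints, add for the circulating T-cell subsets of objective 1.2.3, with memory subsets named, a triplet-minus-doublet estimate of the on-treatment value at C1D21. Adjust for the patient's own baseline, use a log or rank scale if the marker is skewed, and report a 95% CI. Take Week 12 as a further timepoint. An on-treatment value adjusted for baseline also fits the 2.4.5 hypothesis, which is about frequency rather than change.

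In 9.4.1, add the same contrast at C1D21, labelled exploratory, for the tumour markers with a stated cobimetinib hypothesis: PD-L1, CD8:Treg ratio, MHC-I and the other 2.4.3 markers. Keep within-arm changes as description, and state that no conclusion about cobimetinib will be drawn from comparing two within-arm results. Reconcile the arm labels in the 9.4 CD8+ sentence at the same time.

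The cost is SAP wording: samples, assays and patients are unchanged. The downside is intervals about √2 times as wide as those for a change within one arm, before any gain from baseline adjustment, which depends on a correlation the documents do not give.

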### 9.2 Sample Size/Accrual Rate

The study is planned for 64 evaluable subjects (32 subjects per treatment arm). The objective response rate (ORR) of BTCs treated with FOLFOX, anti-PD-1 monotherapy or anti-PDL1+MEKi is around 5%. A clinically meaningful improvement that warrants further study would be a 20% ORR. A Simon two-stage minimax design is planned for each arm. Arm specific type I error is set at 0.1 (one-sided) when evaluating the co-primary endpoints of ORR and PFS. For each arm, 18 patients will be enrolled in the first stage. If none have OR, the accrual to that arm will be terminated. If 1 or more respond, then additional 14 patients will be enrolled (for a total of 32 patients in that arm). If 4 or more patients achieve OR (12.5%) in stage 1 and stage 2 combined, the endpoint is met in that arm. The design yields at least 90% power to detect a true

response rate of at least 20%, with at least .90 probability of a negative result (no more than 3 responses if the true response rate is no more than 5%, for each of the two arms. The chance of early stopping after stage 1 in each arm is 0.4 when the true response rate is 5%.

If both arms meet the response endpoint criteria, the comparison of PFS will be performed. The median progression free survival of BTCs treated with FOLFOX, anti-PD-1 monotherapy, & anti-PDL1+MEKi is 4.0, 2.0, and 3.5 months, respectively. Randomization of 64 patients, with observation of 55 PFS events would yield 90% power to detect an HR = 0.5 (corresponding to 3.5 vs. 7 months median PFS in the doublet and triplet arm, respectively), at the one-sided 0.10 significance level. An observed 40% increase in median PFS for the triplet arm (approximately 1.4 months, assuming an approximately 3.5-month median PFS in the doublet arm; observed HR=0.714) would be sufficient to achieve statistical significance.

Taking into account dropout/study attrition, we anticipate screening between 70-80 patients in order to achieve 32 evaluable patients per treatment arm (N=64) with an anticipated accrual rate of 4 patients/month.

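### With about 2–6 expected responders per arm, the per-arm adjusted logistic models of response in Section 9.4.1 are over-parameterised and need a penalised or exact method with a covariate limit

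*Combined protocol and SAP*

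**What the plan says.** Section 9.4.1 (Analysis of Exploratory Endpoints) treats response as categorical. It characterises the association between response and immunological variables "in each arm, using multivariate logistic regression models, with adjustment for clinical and pathological co-variates that may be associated with response". Effects are to be reported with standard errors and confidence intervals. The section does not name or count the covariates, does not say how the model is fitted, and gives no alternative for sparse data.

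Section 9.2 fixes the amount of information available:

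- Size: "The study is planned for 64 evaluable subjects (32 subjects per treatment arm").
- Reference rate: response to FOLFOX, "anti-PD-1 monotherapy or anti-PDL1+MEKi is around 5" per cent.
- Target: "A clinically meaningful improvement that warrants further study would be a 20% ORR".
- Rule: "For each arm, 18 patients will be enrolled in the first stage", with accrual to an arm ending if none respond. "If 4 or more patients achieve OR (12.5%) in stage 1 and stage 2 combined, the endpoint is met in that arm".

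**The concern.** The information in a logistic model is limited by the smaller outcome group, here the responders. An arm can be declared a success with 4 responders, yet the plan fits a model with a marker and several covariates inside that arm. Two things can go wrong. A covariate pattern can split responders from non-responders (separation), and then at least one odds ratio has no finite maximum-likelihood estimate. Or the fit is finite but biased away from the null, with very wide intervals.

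What is at stake is the link between immune markers and response. Section 2.4.1 states one such hypothesis for CD8+ infiltration. The tissue comes from two biopsies that Section 5.2 labels as research without clinical impact. Section 9.4.1 expects later studies to build on these results, and inflated odds ratios would be a poor base for them.

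**Working it through.** **1. The plan's own design figures reproduce.** For 18 then 32 patients, stopping at 0 of 18 and succeeding at 4 or more of 32, the exact two-stage binomial gives:

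- P(success | 20%) = 0.901 (plan: at least 0.90)
- P(success | 5%) = 0.072, so P(negative | 5%) = 0.928 (plan: at least 0.90)
- P(stop early | 5%) = 0.95^18 = 0.397 (plan: 0.4)

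**2. Expected responders per arm (n × p).** 32 × 0.05 = 1.6; 32 × 0.125 = 4.0; 32 × 0.20 = 6.4. These are expected counts, not limits. The probability of 6 or fewer responders in 32 is 0.999, 0.904 and 0.535 at the three rates, and the probability of 10 or more at 20% is 0.09. Among arms with at least 4 responders, the mean count is 4.4 at a 5% rate and 6.8 at 20%.

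**3. Events per coefficient.** With 2 to 6 responders and 3 to 7 coefficients, the range is 2/7 ≈ 0.3 to 6/3 = 2.

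**4. Failures that need no simulation.**

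- With 0 responders, no logistic model can be estimated.
- With 1 responder, any binary covariate is separated.
- With 2 responders, a three-level factor must have a level with no responder.

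At a 5% rate under the two-stage rule, P(0) + P(1) + P(2) = 0.397 + 0.184 + 0.217 = 0.80.

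**5. Simulated share of arms with no finite fit.** Assumptions: n = 32, marker unrelated to response, continuous covariates N(0,1), binary covariates 50/50, site 25/50/25. Separation was detected by linear programming in 600 to 1,000 datasets per setting.

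| Model | 2 responders | 4 | 6 |
|---|---|---|---|
| marker + 2 continuous | 0.08–0.09 | 0.00 | 0.00 |
| marker + 4 continuous | 0.40–0.43 | 0.04–0.05 | 0.01 |
| marker + 2 binary | 0.79 | 0.26 | 0.06 |
| marker + site | 1.00 | 0.62–0.65 | 0.34–0.36 |
| marker + 1 continuous + 1 binary + site | 1.00 | 0.68 | 0.37–0.38 |

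A separate run with a true marker log-odds ratio of 1.0 gave about 1–4% with continuous covariates only and 3–16% with one continuous and one binary covariate. With site added it gave 37–67% for 6 to 4 responders and 100% for 2.

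**6. Which coefficient is infinite.** For marker + one binary + site with a null marker, some term is infinite in 100%, 67% and 33% of arms with 2, 4 and 6 responders. The marker's own coefficient is infinite in 9%, 0.4% and 0%. With a 1 SD marker effect the marker figures are 18%, 5% and 2%. Only larger models with few responders or strong effects lose the marker in most arms. An example is marker + 2 continuous + 2 binary + site with a 1.5 SD effect: 89%, 61% and 41%.

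**7. Quality of the finite fits.** For n = 32 and a true marker log-odds ratio of 1.0, with separated fits dropped:

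- 4 responders: mean estimate 1.65 (marker + 2 continuous), 1.58 (marker + 1 continuous + 1 binary) and 1.77 (marker + 1 binary + site). The upper 95% limit for the odds ratio is typically 21 to 24 times the lower.
- 6 responders: mean 1.36 to 1.54 over these models, with limits 12 to 14 times apart.
- A second run over 4 to 6 responders gave means of about 1.5 to 2.1. Firth-penalised fits on the same footing averaged about 1.0 and stayed finite under separation.

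Part of this inflation comes from a right tail of large estimates, so a typical single estimate is inflated less than the mean.

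**The case against.** The strongest reply has four parts.

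- **The plan does not say maximum likelihood.** Firth and exact fitting are also logistic regression, and the section allows data inspection and transformation first. This is true, and it makes the repair easy. But a plan that names only logistic regression with standard errors will be run with the default fit unless it says otherwise.
- **Separation depends on covariates the reviewer chooses.** This stands. Site of disease appears in Section 9.3 only as a stratification factor. With 4 to 6 responders, a null marker and a few continuous covariates, separation is about 0–5%. A reader might infer that the per-arm models will usually have no finite estimate; the documents do not support that, because they neither name nor count the covariates.
- **The infinite term is usually a nuisance term.** This also stands for small models that include site. A reader might infer that the marker effect itself could not be estimated, but step 6 shows that this is rare there. It does not cure the inflation and imprecision in step 7.
- **The analysis is exploratory.** Agreed. The overarching aim in Section 9.4.1 is baseline levels and change under treatment. The main correlative comparison, CD8+ infiltration between arms (Sections 2.4.1 and 9.4), uses a t-test or Wilcoxon test and is unaffected.

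The arms that matter most for follow-up are those that meet the response endpoint, with at least 4 responders. That removes the certain failures at 0 to 2 responders, but not the problems at 4 to 6.

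**Conclusion.** The point holds in a limited form. On the trial's own rates, about 2 to 6 responders are expected per arm, and covariate-adjusted maximum-likelihood models fitted within an arm are over-parameterised. Separation is frequent if categorical covariates such as site are included: about 37% to 67% of arms with 6 to 4 responders, and 100% with 2. With continuous covariates only, fits are usually finite, but the mean log-odds ratio is inflated by roughly 50% or more. Across the models tried, the inflation was 36–77% in one set of simulations and about 50–110% in the other.

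These sizes rest on assumed covariate types, the assumed site mix and an assumed true effect. Tissue markers may be available for fewer than 32 patients, since Section 11 limits biopsy to safely accessible tumours. The number is not given. With 20 patients assumed, site models separate about as often or somewhat more often. Blood markers need not shrink in this way.

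No primary or secondary conclusion and no stopping decision is touched, so the priority is low.

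**What to change.** Amend Section 9.4.1 to state that:

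- these exploratory models use Firth-penalised logistic regression with profile-likelihood intervals, or exact logistic regression with exact intervals where the terms are discrete enough for it to work;
- each model holds one immunological marker and at most one covariate, named in advance;
- any arm with fewer than about 3 responders is reported descriptively, without a model.

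A pooled two-arm model with an arm term may be added as a supplement. It should not replace the per-arm results. It assumes the same marker effect in both arms, while Sections 2.4.1 to 2.4.3 hypothesise that cobimetinib changes the immune response. Pooling alone does not remove separation either: with marker, arm and site in 64 patients, simulated separation is 64%, 37% and 20% at 4, 6 and 8 total responders. The penalised or exact fit does most of the work.

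The cost is a few lines of SAP text and less covariate adjustment. No extra patients, samples or visits are needed.
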